10.1 Confounding

Imbalances between groups in important covariates are not expected to be of sufficient magnitude to produce confounding. The primary analysis described above in Section 7 includes a fixed, pre-specified list of covariates. As an additional sensitivity analysis, any baseline demographic or clinical characteristics (see Section 14 below) observed to be imbalanced between HCL or verapamil treatment groups will be added as covariates in the primary analyses. The determination of a meaningful balance will be based on clinical judgement and not a p-value. This assessment of baseline differences will be made blinded to the outcome data.

10.2 Missing Data

It is worth emphasizing that any statistical method for handling missing data makes a number of untestable assumptions. The goal will be to minimize the amount of missing data in this study so that results and conclusions will not be sensitive to which statistical method is used.

To that end, a number of methods will be handle any missing data. As noted above in Section 7, the primary analysis will use the method of direct likelihood. Additional sensitivity analyses will handle missing data by:

- Rubin's multiple imputation
- Multiple imputation with a pattern mixture model
- Available cases only

11. Subgroup Analyses

Subgroup analyses will be conducted separately for the two primary analyses (HCL and verapamil). Interpretation of the analyses will be made with caution and tests only performed if the overall treatment effect from the corresponding primary hypothesis is significant ($P < 0.05$). The general approach for these exploratory analyses will be to add an interaction term for the subgroup factor by treatment into the model used for the primary analyses. A similar analysis will be repeated for time in range 70-180 mg/dL. The following baseline factors will be tested:

- Age (<12 , ≥ 12 years old)

453 • Sex
454 • Tanner staging (I vs II-V)
455 • Time since diagnosis at randomization
456 • Presence of DKA at diagnosis at randomization
457 • HbA1c at randomization
458 • C-Peptide AUC at randomization
459 • Antibody levels at screening
460 • Pre-existing autoimmune diseases

461
462 The p-value for any categorical variable will only be calculated if there are a minimum of 10
463 subjects per treatment group.

464

465 **12. Additional Exploratory Analyses**

466 **12.1 C-peptide**

467 The following tabulations will be performed at 13, 26, 39, and 52 weeks by treatment group:

468 • Peak C-peptide during a 2-hour MMTT
469 • Percentage of patients with peak C-peptide ≥ 0.2 pmol/ml

470

471 **12.2 HbA1c**

472 The percent of participants with HbA1c $< 6.5\%$ and percent $< 7.0\%$ will be tabulated at 13, 26, 39,
473 and 52 weeks by treatment group.

474

475 **12.3 CGM Metrics**

476 For daytime and nighttime, each CGM metric listed in Section 5 will be tabulated accordingly at
477 6, 13, 26, 39, and 52 weeks by treatment group.

478

479 **12.4 Insulin**

480 The following tabulations will be performed at 6, 13, 26, 39, and 52 weeks by treatment group:

481 • Total daily insulin dose per kg
482 • Basal:Bolus ratio

483

484 **12.5 C-peptide and Glycemic Control**

485 To evaluate the relationship between C-peptide and glycemic control, scatterplots will be created
486 at each time of the following factors on the horizontal axis, with C-peptide AUC on the vertical
487 axis:

488 • CGM-measured % in range 70-180 mg/dL

- CGM-measured % above 180 mg/dL
- CGM-measured % below 70 mg/dL
- CGM-measured % below 54 mg/dL
- Glucose CV
- Mean HbA1c
- HbA1c CV
- Insulin dose adjusted percent time in range (70-180 mg/dL)

A longitudinal regression model will be fit with C-peptide as the dependent variable and time in range as the predictor variable separately for the HCL and non-HCL arms pooled over verapamil arms. Curves will be constructed for HCL and non-CL analogous to the DCCT analysis of HbA1c and retinopathy [5]. Similar curves will be constructed for verapamil and placebo arms and all four combinations if interaction is detected (see Section 9 above).

Similar to the model described above, a longitudinal regression model will be used to compare C-peptide between those who achieved high (> 85%) vs lower (< 65%) time in range separately for the HCL and non-HCL arms pooled over verapamil arms. The cutoffs for the high and low time in range groups may be adjusted after reviewing the distribution.

Additional exploratory analyses will be done using the other CGM metrics (and HbA1c) listed above and various combinations thereof. Model selection techniques with shrinkage (e.g., LASSO) will be used to determine the combination of CGM metrics that best predict C-peptide, potentially adjusting for confounding factors such as age and sex. Since these are exploratory analyses, the statistical methods used may be data-driven depending on results observed from initial analyses.

13. Safety Analyses

All reported adverse events will be sorted by date and listed.

For SH events, DKA events, and serious adverse events (excluding DKA and SH events), appropriate summary statistics for the following outcomes will be tabulated by treatment group.:

- Number of events per participant
- Number of participants with at least one event
- Incidence rate per 100 person-years

As described above for the efficacy analyses, safety comparisons of HCL versus non-HCL will combine cohorts A and B, and comparisons of verapamil versus placebo will be restricted to cohort A. Formal statistical comparisons will only be performed if at least 5 events occur during the study. The proportion of participants with at least one event will be compared using generalized estimating equations (GEE) logistic regression adjusting for age, and time from diagnosis to randomization. Clinical site will be treated as a repeated factor using a compound symmetry covariance structure. A risk-adjusted difference and 95% confidence interval for the

531 percentages will be calculated using the method of Kleinman and Norton (4). If the model does
532 not converge then Barnard's test will be used instead. Incidence rates will be compared using a
533 Poisson regression model adjusting for age and time from diagnosis to randomization as fixed
534 effects and clinical site as a random effect. Models for DKA outcomes will also include presence
535 or absence of DKA at diagnosis as a covariate.

536 For SH events, separate analyses also will be done for the outcomes listed above that will only
537 include events that resulted in seizure or a loss of consciousness (if there are at least 5 such
538 events).

539 For the verapamil vs. placebo comparison the frequency of adverse events stratified by MeDRA
540 class will be reported.

541

542 **14. Protocol Adherence and Retention**

543 Tabulations and figures by treatment group to assess protocol adherence will include:

- 544 • Flowchart accounting for all subjects according to treatment group for all visits
- 545 • Visit completion rates for each follow up visit
- 546 • Protocol deviations
- 547 • Numbers and reasons for unscheduled visits and phone calls

548

549 HCL system use, verapamil, and placebo adherence will be tabulated at each time point and
550 reported in a table.

551

552 **15. Baseline Descriptive Statistics**

553 Baseline demographic, outcome, and covariate characteristics will be summarized with counts
554 (percentages), mean (SD), median (quartiles) as appropriate to the distribution. There will be two
555 tables, one for HCL vs. non-HCL in the combined A+B cohort, and another for verapamil vs.
556 Placebo, including only cohort A. For each of these tables, there will be a total column.

- 557 • Age
- 558 • Gender
- 559 • Race
- 560 • Ethnicity
- 561 • Annual Household income
- 562 • Education
- 563 • Health Insurance
- 564 • DKA at diagnosis
- 565 • HbA1c lab
- 566 • C-peptide AUC
- 567 • Time since diagnosis at randomization
- 568 • Tanner Staging (I vs II-V)

569 • Blood pressure (systolic/diastolic)
570 • BMI
571

572 **16. Device Issues**

573 All reportable device issues occurring during the study will be tabulated and reported in a table.

574

575 **17. Planned Interim Analyses**

576 No formal interim analyses or stopping guidelines are planned for this study.

577 The DSMB will review data for safety per the DSMB Standard Operating Procedures
578 approximately every six months. The data to be reviewed will include information regarding
579 adverse events, device issues, and protocol adherence/deviations as they may relate to participant
580 safety.

581

582

583 **18. Multiple Comparisons**

584 For the primary analyses, no adjustments for multiplicity will be made because two different
585 interventions are being tested separately.

586 For secondary analyses the false discovery rate (FDR) will be controlled using the adaptive
587 Benjamini-Hochberg procedure separately for the HCL and verapamil analyses. For these
588 analyses, the adjusted p-value and 95% confidence interval will be reported.

589 There will be no adjustments for multiple comparisons on safety analyses, sensitivity analyses,
590 or per protocol analyses.

591

592 **18. References**

593 1. Lachin JM, McGee PL, Greenbaum CJ, et al. Sample size requirements for studies of
594 treatment effects on beta-cell function in newly diagnosed type 1 diabetes. *PLoS One*.
595 2011;6(11):e26471.

596 2. Ovalle F, Grimes T, Xu G, et al. Verapamil and beta cell function in adults with recent-onset
597 type 1 diabetes. *Nature medicine*. 2018;24(8):1108-1112.

598 3. Greenbaum CJ, Beam CA, Boulware D, et al. Fall in C-Peptide during first 2 years from
599 diagnosis: evidence of at least two distinct phases from composite type 1 diabetes TrialNet data.
600 *Diabetes* 2012; 61(8): 2066-2073.

601 4. Kleinman LC, Norton EC. What's the risk? A simple approach for estimating adjusted risk
602 measures from nonlinear models with logistic regression. *Health Services Research* 2009; 44(1):
603 2009 Feb.

604 5. Diabetes Control and Complications Trial Research Group: The relationship of glycemic
605 exposure (HbA1c) to the risk of development and progression of retinopathy in the Diabetes
606 Control and Complications Trial. *Diabetes*, 1995; 44:968-983.

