2.1 Participant Recruitment and Enrollment

The study will recruit two cohorts—Cohort A will include participants who weigh ≥ 30 kg at Screening and Cohort B will include participants who weigh < 30 kg at Screening.

Enrollment will proceed with the goal of at least 98 participants in Cohort A and 33 in Cohort B being randomized and at least 88 in Cohort A and 30 in Cohort B completing the trial.

Participants who have signed consent and started the screening process may be permitted to continue into the trial, if eligible, even if the randomization goal has been reached.

Potential study participants will be identified clinically from the general pediatric diabetes new-onset population and recruited from ~6 clinical centers in the United States. All eligible participants will be included without regard to gender, race, or ethnicity. There is no restriction on the number of participants to be enrolled by each site toward the overall recruitment goal. The maximum number to be enrolled for screening for the study (meaning that informed consent is signed) is 200.

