1453 Secondary analyses for HCL/intensive care vs. non-HCL/standard care and verapamil vs. placebo
1454 will be performed and described in the SAP.

1455 **10.8 Safety Analyses**

1456 All adverse events will be listed by cohort. Events also will be listed separately for the HCL/intensive
1457 and non-HCL/standard care arms since differential reporting may occur due to the many additional
1458 study contacts occurring in HCL participants.

1459
1460 In all safety analyses comparing the HCL/intensive to the non-HCL/standard care group, Cohorts
1461 A and B will be combined.

1462
1463 For SH events, DKA events, and hospitalizations, the following outcomes will be compared
1464 between treatment groups if there are at least 5 events that occur during the study:

- Number of events per participant
- Number of participants with at least one event
- Incidence rate per 100 person-years

1465
1466 For the count outcomes and the incidence rates, a Poisson regression model will be used. All
1467 models will adjust for site as a random effect. Additionally, the models for the DKA outcomes
1468 will adjust for the presence or absence of a DKA event at diagnosis.

1469
1470 For SH events, separate analyses also will be done for the outcomes listed above that will only
1471 include events that resulted in seizure or a loss of consciousness.

1472 **10.9 Intervention Adherence**

1473 HCL system use, verapamil, and placebo adherence will be tabulated at each time point and
1474 reported in a table.

1475 **10.10 Protocol Adherence and Retention**

1476 Tabulations and figures by treatment group to assess protocol adherence will include:

- Flowchart accounting for all participants according to treatment group for all visits
- Visit completion rates for each follow up visit
- Protocol deviations
- Numbers and reasons for unscheduled visits and phone calls

1477 **10.11 Baseline Descriptive Statistics**

1478 Baseline demographic and clinical characteristics will be tabulated overall, by cohort, and by
1479 treatment group.

1480 **10.12 Device Issues**

1481 All reportable device issues occurring during the study will be tabulated and reported in a table.

1482 **10.13 Planned Interim Analyses**

1483 No formal interim analyses or stopping guidelines are planned for this study.

1484
1485

1492 The DSMB will review data for safety per the DSMB Standard Operating Procedures approximately

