374 listed above and will be limited to the 24 hour versions (analysis of daytime and nighttime versions
375 will be descriptive only). Analysis will follow the method described above with three exceptions:

- 376 • The longitudinal model will not be constrained because no baseline values will be
377 available.
- 378 • The unconstrained longitudinal model will include 6 week values.
- 379 • For verapamil vs. placebo comparisons the type of CGM sensor used (Medtronic, Dexcom)
380 will be included as a covariate in the models. This covariate will be allowed to differ within
381 subject if the participant changes devices between visits. If the participant switches sensors
382 in the 28 day period used to calculate CGM metrics, data from both sensors will be used to
383 calculate metrics and the value for the sensor covariate will be set equal to the sensor which
384 contributed the most data.

385
386 It is likely that percentage of sensor values below 54 mg/dL and possible that the percentage of
387 sensor values above 250 mg/dL will have a skewed distribution. The other CGM metrics are
388 anticipated to have an approximate normal distribution. As described above for the primary
389 analysis, robust regression with M-estimation will be used to analyze skewed outcomes.

390
391 The percentage of patients with $\geq 70\%$ of sensor values from 70 to 140 mg/dL will be analyzed
392 using generalized estimating equations (GEE) logistic regressions adjusting for baseline HbA1c,
393 age, time from diagnosis to randomization. Clinical site will be treated as a repeated factor using
394 a compound symmetry covariance structure. A risk-adjusted difference and 95% confidence
395 interval for the percentages will be calculated using the method of Kleinman and Norton (4). This
396 analysis will be available cases only. There will be no imputation of missing data.

397 398 9. Interaction Analyses

399 A factorial design is being used for this study because it is believed to be unlikely that the device
400 (HCL) and drug (verapamil) would interact with each other. An interaction test will be
401 conducted to explore this assumption. This analysis will be limited to cohort A. Note that this
402 study has not been powered to detect interaction. Thus, this analysis is considered exploratory
403 and no primary conclusions about the efficacy of either HCL or verapamil will be based solely

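### SAP 8.5 tests a 70–140 mg/dL responder outcome that the SAP lists nowhere and that SAP 8.1 leaves no room for; separately, the GEE models with about six sites name no variance estimator

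*SAP*

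**What the plan says.** **Responder outcome.** SAP 2 (outcomes added to the protocol) and SAP 5 (outcome list) both define a CGM responder as a patient with at least 70% of readings in 70–180 mg/dL. The 70–140 range appears in those sections only as a continuous percentage of time. The last paragraph of SAP 8.5 then assigns a GEE logistic regression, with an adjusted risk difference and 95% interval, to the percentage of patients with at least 70% of readings in 70–140 mg/dL. It gives no visit. SAP 8.1 restricts formal comparisons of the other secondary outcomes, at 26 and 52 weeks, to HbA1c, daily insulin per kg and seven continuous CGM indices. SAP 18 applies an adaptive Benjamini-Hochberg procedure to the secondary analyses, separately for HCL and verapamil.

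**GEE models.** SAP 13 compares the proportion of participants with at least one event by GEE logistic regression adjusted for age and time from "diagnosis to randomization. Clinical site will be treated as a repeated factor using a compound" symmetry structure. SAP 8.5 uses the same device, adjusting for baseline HbA1c, "age, time from diagnosis to randomization. Clinical site will be treated as a repeated factor using" that structure. Participants are "recruited from ~6 clinical centers in the United States"; the Protocol Summary says six. On safety, "Formal statistical comparisons will only be performed if at least 5 events occur", and if the model does "not converge then Barnard's test will be used instead". "Models for DKA outcomes will also include presence" or absence of DKA at diagnosis. Risk differences follow Kleinman and Norton. Neither section says whether standard errors are empirical or model-based, which reference distribution applies, or whether a small-sample correction is made. SAP 18 adds: "There will be no adjustments for multiple comparisons on safety analyses".

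**The concern.** The 8.5 sentence is operative text: a programmer following it would test an outcome that the SAP never defines as an endpoint. SAP 8 calls for descriptive summaries of the outcomes listed in SAP 5, so the responder that is tabulated (70–180) would not be the one that is tested (70–140). A programmer following 8.1 would test no responder outcome at all. The choice also decides how many p-values enter the false discovery rate adjustment, and so can move the adjusted p-values of other secondary outcomes.

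The GEE matter is one of under-specification. An empirical (sandwich) variance is estimated from between-cluster variation, and about six clusters are few for the usual normal approximation. Software offers several variances that can disagree here. The outcomes in SAP 13 include severe hypoglycemia and DKA, the key safety outcomes, so the choice should not be left open until the data are in hand.

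**Working it through.** **Part 1: the passages side by side**

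| Place | Responder range | Formal test? |
|---|---|---|
| SAP 2 | 70–180 mg/dL | not stated |
| SAP 5 | 70–180 mg/dL | not stated |
| SAP 8.1 | no responder outcome | no (closed list) |
| SAP 8.5 | 70–140 mg/dL | yes, by GEE, no visit given |

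Effect on multiplicity, reading SAP 18 as one family per intervention:
- C-peptide AUC at 13, 26 and 39 weeks: 3 tests.
- HbA1c, insulin and 7 CGM indices at 2 visits: 9 × 2 = 18 tests.
- Total under 8.1: 3 + 18 = 21. With a responder test at 26 and 52 weeks: 23.

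The plain Benjamini-Hochberg adjusted p-value at rank i is based on p(i) × m / i. Going from m = 21 to 23 multiplies it by 23/21 = 1.10 if ranks are unchanged, and by less if a responder p-value ranks ahead. The adaptive version replaces m by an estimated number of true nulls, so the exact shift depends on the data.

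**Part 2: GEE with about six sites**

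The documents state no operating characteristic for these tests. Their only power figures concern the primary outcome, and they reproduce: effect 0.126 and SD 0.18 need 43 per arm (86, against 88 stated); 88/0.90 = 97.8, so 98; and 64 against 54 completers give 96.4–96.6% power (96% stated).

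The sandwich variance is A⁻¹BA⁻¹, where B sums one squared score contribution per site: six terms. The SAP 13 model has 4 coefficients (intercept, treatment, age, time from diagnosis), or 5 for DKA; the 8.5 model has 5. Sites minus coefficients is therefore 6 − 4 = 2 or 6 − 5 = 1.

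Inputs from the documents: about six sites; N = 131 (71 against 60) and N = 98 (1:1); randomization stratified by site; a trigger of at least 5 events; compound symmetry. Assumptions not in the documents:
- Simulation A: event risk 4.5, 8, 15 or 25%; site SD 0.3 (logit); equal or unequal sites; with or without a DKA covariate (prevalence 40%, odds ratio 2); recurrence of 1 + Poisson(0.2) events per affected participant. This gives 32 null scenarios of 2,500 datasets.
- Simulation B: event risk 6–50%, plus a sparse set at 4–5%; site SD 0 or 0.5 (sparse set 0); equal sites or 30:25:20:12:8:5; trigger of 5 affected participants; 4,000 datasets per scenario.

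Type I error at nominal 5%; coverage of the 95% risk-difference interval:

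| Method | A | B, 6–50% | B, 4–5% |
|---|---|---|---|
| Uncorrected sandwich, z | 9.3–16.3%; 83.0–88.2% | 8.4–15.8%; 83.4–88.8% | 6.4–12.2%; 85.6–88.0% |
| Model-based, z | 0.3–5.4%; 93.5–97.1% | 1.5–5.0%; 94.3–96.2% | 1.8–2.2%; 95.8–96.2% |
| Mancl-DeRouen, t on 5 df | 1.5–4.3%; 95.8–98.2% | 1.4–3.9%; 95.7–98.2% | 0.8–2.1%; 96.4–98.4% |

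Further checks:
- A model of the 8.5 type (three covariates, N = 88–118) gave 13.1–15.0% and coverage 84.8–86.4% for the sandwich z-test.
- With 5 or 7 equal sites the sandwich z-test gave 16.6% and 11.9%.
- Standard software (statsmodels, N = 131) gave 11.5% and 14.4% for the sandwich against 3.4% and 5.3% for model-based variance on the same data. A smaller run of 500 datasets per scenario gave 9–18% against 2.5–5.5%; its simulation standard error is up to √(0.18 × 0.82/500) = 1.7 points.
- In simulation A, with a true difference of 9.7–10.8 points, power was 11.0–18.3% for Mancl-DeRouen t and 23.7–33.5% for model-based variance. At N = 131, risk 8% and unequal sites, median interval widths were 25.3 and 18.5 points, a ratio of 25.3/18.5 = 1.37.

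**The case against.** **On the responder outcome.** It can be said that 70–140 was meant, because SAP 2 adds time in 70–140 as a new outcome and 8.1 tests it. That outcome is the continuous percentage, with no 70% threshold, and nothing else in the SAP names a 70–140 responder. It can also be said that 8.1 makes an exception for 8.5. The exception covers the modelling approach, not the list, and 8.5 itself refers back to the selected indices in that list. The conflict stands whichever range was intended.

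**On the GEE.** A reader might infer that the planned safety tests have a false-positive rate of up to 16%. The documents do not support that. They do not choose the uncorrected sandwich z-test, and with model-based variance the same GEE holds its level. The inflation is also smaller where events are sparse, which matters with a trigger of 5 events: in the sparse set of simulation B, up to 47% of datasets had too few events or no usable fit. The safety reading does not rest on these tests alone, since event rates are also compared by Poisson regression and the DSMB reviews safety separately. These points limit the size of the problem but do not supply the missing specification. Barnard's test answers non-convergence only, and Kleinman-Norton fixes how the risk difference is computed, not the variance of the coefficients.

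A reader might also infer that the GEE departs from Protocol 10.8, which adjusts for site as a random effect. That sentence directly follows "For the count outcomes and the incidence rates, a Poisson regression model will be used" and can be read as covering those Poisson models only. Protocol 10.1 leaves further detail to the SAP. No departure is shown.

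Nor do the simulations single out one remedy. Mancl-DeRouen with t is conservative and has about half the power of model-based variance, a real cost for safety outcomes.

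**Conclusion.** The main point holds without any assumption: SAP 8.5 is wrong as written against SAP 2, 5 and 8.1, and the false discovery rate family is undetermined as a result (21 or 23 tests per intervention on the reading above).

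The lesser point holds conditionally. If the uncorrected sandwich z-test is used with about six sites, type I error is roughly 8–16% (about 6–12% at event proportions of 4–5%) and 95% risk-difference coverage roughly 83–89%. Model-based variance gives about 0.3–5.4% and 94–97%. Event risks, site sizes and site variance are assumptions, so the ranges matter more than any single value. Only the secondary and safety proportions are affected. The primary C-peptide analyses, the Poisson rate comparisons and the sample size are not.

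**What to change.** 1. In the GEE sentence of SAP 8.5, change the range to 70–180 mg/dL. Then either add that responder outcome, at 26 and 52 weeks, to the SAP 8.1 list, so that its p-values clearly enter the SAP 18 procedure, or delete the 8.5 test and report the outcome descriptively.
2. In SAP 13, and in 8.5 if its test is kept, state that the uncorrected sandwich z-test will not be used. Name in advance one method that holds its level at about six clusters, and use the same variance and reference distribution for the Kleinman-Norton interval. The choice is the sponsor's:
   - model-based variance has more power but relies on the working correlation;
   - Mancl-DeRouen variance with t on (sites − 1) df is conservative, with wider intervals and the lower power shown above.

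Under either method a non-significant safety comparison should not be read as evidence of no difference.

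The cost is SAP wording only, with no new data. SAP 2.0 was issued with follow-up ongoing; the change should be dated before any treatment-group results are seen.
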